# Statistical Analysis Plan

A Multi-center Outcomes Clinical Study of the PyroTITAN™ HRA Shoulder Implant in Humeral Head Resurfacing

Number: CP-HRA-002  
ST: ST1159  
Version: 1.0 05/Oct/2023  
Page: 19 of 19

Events will be summarised by the AE/SAE/ADE/SADE/USADE classifications derived from the Investigator assessment of the event. In the case of disagreements, a separate summary of event classifications made by the Sponsor will also be provided.

In addition, AEs will be summarised by; severity (intensity), relationship to study device, relationship to procedure, outcome and duration of adverse event at trial discontinuation.

A listing will be provided which details subject number, AE description, start date, end date/ongoing, classification, severity, seriousness, relationship to device, relationship to procedure, anticipation, actions taken, outcome and whether study participation was discontinued due to the event.

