### Adverse events

Adverse events are recorded by the Investigator and then reviewed by the Adverse Events Monitoring Board (AEMB) at Smith + Nephew and documented in RAVE. The most stringent classification will be presented and reported. Investigator assessments will be provided in listings.

Investigators do not classify events, S+N use the Investigator assessment to classify the event as follows:

- An event will be classified as "related" if the relationship if rated as possible/probable/definite to the Device and/or procedure from the investigator assessment, otherwise it will be classified as "not related".
- An event will be classified as an ADE if the event is related to the study device and/or procedure.
- An event will be classified as an SAE if the event is serious.
- An event will be classified as an SADE if it is an ADE which is also serious.
- An event will be classified as a USADE if it is an SADE which is also unanticipated.
- Otherwise, the event will be a non-device, non-procedure related, non-serious AE.

For adverse events that have been resolved, duration of adverse event is calculated as end date minus start date.

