# Statistical Analysis Plan

A Multi-center Outcomes Clinical Study of the PyroTITAN™ HRA Shoulder Implant in Humeral Head Resurfacing

Number: CP-HRA-002  
ST: ST1159  
Version: 1.0 05/Oct/2023  
Page: 13 of 19

Due to system updates, checks need to be performed to ensure the most stringent classification is being reported. When comparing Investigator assessments (classifications as above) with AEMB classifications, the most stringent classification should be reported as follows:

Investigator assessment	AEMB classification	Most stringent
AE	SAE	SAE
SAE	AE	SAE
AE	ADE	ADE
ADE	AE	ADE
ADE	SADE	SADE
SADE	ADE	SADE
SAE	SADE	SADE
SADE	SAE	SADE
SADE	USADE	USADE
USADE	SADE	USADE

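### SAP 7.4 requires the most stringent adverse event class to be reported, but SAP 7.12 summarises events by the investigator-derived class, so nested SAE, ADE, SADE and USADE counts can be too low

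*SAP*

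**What the plan says.** SAP 7.4, under Adverse events, describes two assessments of each event. The investigator records and assesses it, and the sponsor turns that assessment into a class: "Investigators do not classify events, S+N use the Investigator assessment to classify the event as follows". The AEMB also reviews the event and gives its own class.

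On reporting, 7.4 says: "The most stringent classification will be presented and reported". The next sentence reads: "Investigator assessments will be provided in listings". It then explains that, because of system updates, "checks need to be performed to ensure the most stringent classification is being reported", and introduces a table of ten investigator/AEMB disagreements with the words "the most stringent classification should be reported as follows".

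SAP 7.12, Analysis of Safety Endpoint(s), sets the tables out differently: "Events will be summarised by the AE/SAE/ADE/SADE/USADE classifications derived from the Investigator assessment of the event". It continues: "In the case of disagreements, a separate summary of event classifications made by the Sponsor will also be provided". Section 7.12 refers neither to the most stringent class nor to the table in 7.4.

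**The concern.** A programmer cannot tell from the SAP which class feeds the AE/SAE/ADE/SADE/USADE summary. Section 7.4 points to the higher of the two classes for each event, and 7.12 points to the investigator-derived one. Wherever the AEMB rates an event more severely, the two instructions give different tables from the same data, and the rule in the analysis section is the less conservative.

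This matters because the study is uncontrolled and unblinded, and monitoring safety is part of its stated purpose (protocol 11.2). SAP 7.14 adds a 5-year interim analysis so that 2- and 5-year data can be published, so the chosen rule may reach print.

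**Working it through.** The plan states no figure to reproduce. The check compares the two rules and then counts over the rows of the 7.4 table.

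**Inputs.** The ten rows in SAP 7.4, written as investigator / AEMB → most stringent:

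- AE/SAE → SAE and SAE/AE → SAE
- AE/ADE → ADE and ADE/AE → ADE
- ADE/SADE → SADE and SADE/ADE → SADE
- SAE/SADE → SADE and SADE/SAE → SADE
- SADE/USADE → USADE and USADE/SADE → USADE

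**Step 1: which assessor is lower.** The investigator-derived class is below the most stringent class in 5 rows (the first of each pair above). The AEMB class is below it in the other 5.

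**Step 2: counts with one event per row.** This illustrates the mechanism and does not estimate its size. Nested counting means that a USADE also counts as a SADE, and a SADE also counts as an SAE and an ADE.

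| Nested count | Investigator | AEMB | Most stringent |
|---|---|---|---|
| SAE | 6 | 6 | 8 |
| ADE | 6 | 6 | 8 |
| SADE | 4 | 4 | 6 |
| USADE | 1 | 1 | 2 |

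For example, the investigator SAE count is 2 SAE + 3 SADE + 1 USADE = 6. The most stringent count is 2 SAE + 4 SADE + 2 USADE = 8. The investigator and AEMB columns are identical and both fall short. The most stringent class is a maximum taken event by event, and two separate summary tables do not determine it.

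A smaller example shows the same. Suppose 3 events are called serious only by the investigator and 3 others only by the AEMB. Each assessor's table then shows 3 of these disputed events as serious, while the 7.4 rule gives 3 + 3 = 6.

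**Step 3: does the direction depend on how events are counted?** Yes. With one exclusive label per event, the same ten rows give, for investigator against most stringent: AE 2 against 0, SAE 2 against 2, ADE 2 against 2, SADE 3 against 4, USADE 1 against 2. An upgrade from SAE to SADE removes an event from the SAE line, so a single line can move either way. Under nested counting, the investigator-based SAE, ADE, SADE and USADE counts can only equal or fall below the most stringent ones. The SAP does not say which applies. The definitions in 7.4 build a SADE from an ADE, which suggests nesting, but the pair table gives each event one label.

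**Step 4: is the 7.4 table complete?** Five classes give 5 × 4 = 20 ordered disagreements, and the table covers 10. Missing in both directions are AE/SADE, AE/USADE, SAE/USADE, ADE/USADE and SAE/ADE. The first four follow from the 7.4 definitions, since one class contains the other. SAE against ADE does not: one is serious, the other is related, and neither outranks the other.

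**The case against.** The best defence is that 7.12 hides little. Where the assessors disagree it requires a sponsor summary as well, and it also requires an event listing that includes classification. AEMB upgrades would therefore be visible. That stands as partial mitigation. The text also does not say whether the sponsor summary shows the AEMB class or the most stringent class, since the sponsor handles both. If it shows the latter, the required counts do appear, though in a secondary table and only in case of disagreement. The AEMB reading is the more natural one.

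It is also fair to say that the reach is limited. No hypothesis test uses these classes. The components of the primary endpoint are determined from removal or revision, complication forms and adverse events for chronic dislocation (SAP 7.4), not from the SAE or SADE label.

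Three stronger readings are tempting, and the documents do not support them:

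- A reader might infer that 7.4 confines investigator assessments to listings and so forbids an investigator-based table. It says that they will be listed, not that they may appear nowhere else.
- A reader might infer that the choice of rule will be made with the disagreements in view. The SAP names table shells as a related document (section 2). These may settle the source and are not available here. What can be said is that the SAP text leaves it open.
- A reader might infer that serious events will be undercounted, perhaps by half as in the 3 + 3 example. That example assumes symmetric disagreement and leaves out events that both assessors call serious.

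**Conclusion.** The two sections conflict and nothing in the documents reconciles them. For every event that the AEMB classes more stringently, the summary that 7.12 bases on the investigator-derived class falls below what 7.4 requires. With nested counting this can make the SAE, ADE, SADE and USADE counts too low. On the natural reading, the sponsor summary shows the upgrades but not the most stringent counts.

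The conclusion rests on two conditions: that the AEMB upgrades at least one event, and that counts are nested. If the AEMB never upgrades an event, the investigator-based counts equal the most stringent ones. The size cannot be derived, because the documents give neither event counts nor a disagreement rate. This is worth correcting because it affects reported safety counts, but it does not touch the primary analysis.

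**What to change.** In SAP 7.12, make the most stringent classification from 7.4 the source of the main AE/SAE/ADE/SADE/USADE table. Give the investigator-derived and AEMB classes as supporting tables or listings, and name the AEMB class explicitly where the text now refers to the sponsor's. State that counts are nested, so that a SADE is also counted as an SAE and as an ADE.

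In SAP 7.4, complete the pair table. AE/SADE, AE/USADE, SAE/USADE and ADE/USADE can be filled in from the existing definitions. SAE/ADE needs a stated rule. One option is to take seriousness and relatedness each from whichever assessor is more stringent. That would make the event a SADE, a class that neither assessor gave, so it is a policy choice for the sponsor to make openly.

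The cost is SAP wording and one derived variable, with no change to data collection. With nested counting, the reported counts will be the same or somewhat less favourable than under the present 7.12.

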## **11.3 Sample Size and Power Analysis**

The original sample size in this study was 150 enrolled subjects. Additional proof testing and improvements in the device inspection process were employed during the study, at which time it was determined that an additional cohort of subjects was necessary. We are now comparing a cohort of subjects enrolled after these changes to the original cohort of subjects.

With an expected attrition rate of 10% per annum, this will yield an evaluable sample size of 52 shoulders at ten years ( $150 * 0.9^{10} = 52.3$ , where 0.9 or 90% is the number expected to be retained from one year to the next). Based on past experience, we may obtain clinical follow-up on this number of shoulders, but we may obtain radiographic follow-up on as few as two-thirds of these shoulders (about 35 shoulders). This remaining number of evaluable shoulders with clinical and radiographic follow-up is adequate to establish a reliable ten-year survival estimate of survival for hemi arthroplasty (Dorey and Amstutz, 1986).

For the new cohort, the sample size is calculated based on the non-inferiority of the study device. The success rate for the study device is 96.1% from the original population and is used as reference rate. Therefore, for a conservative success rate of 96.1% of the study device is used in the study. The non-inferiority margin  $\delta$  of -0.033 is chosen in the study. 212 subjects are required to achieve  $100(1 - \beta) \% = 80\%$  power to detect non-inferiority at the Significance level of  $\alpha = 0.05$ . To account for 10% lost to follow-up, the

total number of additional subjects is 237. Therefore, the estimated enrollment for the study will be 387 subjects.

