### **11.9 Other Endpoints**

The following will be analyzed at the end of the trial:

Adverse Events including, but not limited to:

- Infection
- Loss of fixation
- Breakage
- Dislocations
- Revisions

Data will be entered, verified and validated using a computer database system. Both the data management and statistical analysis will be performed by Ascension Orthopedics, Inc. Descriptive statistics of patient demographic details will be calculated over all patients. Pre-operative values of outcome variables will be compared to postoperative values at various time points. For interval level data, t-tests will be used; for ordinal level data (ranked data) the Wilcoxon matched-pairs signed-ranks test will be employed, and chi-square or Fisher's exact tests will be used for categorical data. Correlation coefficients may also be employed to determine whether preoperative variables are related to outcome variables.

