## 5.4 Safety Endpoint(s)

Adverse Events including, but not limited to:

- Infection
- Loss of fixation
- Breakage
- Dislocations
- Revisions

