# Statistical Analysis Plan

A Multi-center Outcomes Clinical Study of the PyroTITAN™ HRA Shoulder Implant in Humeral Head Resurfacing

Number: CP-HRA-002  
ST: ST1159  
Version: 1.0 05/Oct/2023  
Page: 8 of 19

- **Safety Population (SAF)**, including all subjects who have received any study treatment.

All safety analyses will utilise the SAF Population. All non-safety related endpoints will be analysed using both the FAS and PP analysis populations.

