## Statistical Analysis Plan

A Multi-center Outcomes Clinical Study of the PyroTITAN™ HRA Shoulder Implant in Humeral Head Resurfacing

Number: CP-HRA-002  
ST: ST1159  
Version: 1.0 05/Oct/2023  
Page: 15 of 19

$H_a$  = Alternative hypothesis that the success rate in the investigational group is non-inferior to the reference rate

$\delta$  = Non-inferiority margin pre-specified to be 3.3%.

The survival rate (the clinical success rate) will be calculated and the associated 95% exact confidence interval presented. If the upper 95% confidence limit is greater than the reference rate minus the non-inferiority margin ( $96.1 - 3.3 = 92.8\%$ ) then non-inferiority of the observed rate to the reference rate to within a 3.3% margin can be concluded.

Additionally, survival rate (the clinical success rate) and the associated 95% exact confidence interval at 2 and 5 years will be calculated and presented.

If data allows, time-to-event curves for device survival will be estimated using the Kaplan-Meier technique. For analysis of device survival, those lost to follow up or withdrawn from the study for reasons other than device revision or removal will be regarded as censored observations.

The primary analysis of this endpoint is to be carried out using the FAS population. The same analysis will be carried out on the PP population as supporting analyses.

As an additional analysis, the primary endpoint will be summarised for PP1 and PP2 populations in order to compare the cohort of subjects enrolled after the device changes to the original cohort of subjects.

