## 7.12 Analysis of Safety Endpoint(s)

### Adverse events

The number of events and the number of subjects reporting: adverse events (AEs), serious adverse events (SAEs), adverse device effects (ADEs), serious adverse device effects (SADEs), and unanticipated serious adverse device effects (USADEs) will be summarised.

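### SAP 7.12 plans no summary by event type for the five named safety endpoints, and the safety population is not split by cohort

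*SAP*

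**What the plan says.** **The endpoints.** Protocol 11.9 opens with "The following will be analyzed at the end of the trial" and lists infection, loss of fixation, breakage, dislocations and revisions. SAP 5.4 repeats the same five as the safety endpoints, under "Adverse Events including, but not limited to".

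**The analysis.** SAP 7.12 gives numbers of events and of subjects for AEs, SAEs, ADEs, SADEs and USADEs. It then states that "AEs will be summarised by; severity (intensity), relationship to study device, relationship to procedure, outcome and duration of adverse event at trial discontinuation". The nature of the event appears in one place: "A listing will be provided which details subject number, AE description, start date, end date/ongoing, classification, severity, seriousness", and further columns. SAP 7.4 derives class, relatedness and duration, but no variable for event type. SAP 7.13 plans no other summaries. SAP 7.14 lists one change from the protocol, the added 5-year interim analysis, and nothing on this point.

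**The population.** SAP 7.2 states: "All safety analyses will utilise the SAF Population". That set is everyone who received study treatment. Cohort flags exist only through the two per-protocol subsets PP1 and PP2, which serve the primary endpoint.

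**The cohorts.** After describing the added proof testing and the better device inspection, Protocol 11.3 says: "We are now comparing a cohort of subjects enrolled after these changes to the original cohort of subjects". SAP 7.9 carries this out for one outcome: "the primary endpoint will be summarised for PP1 and PP2 populations".

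**The concern.** A safety endpoint that is named and promised for analysis should lead to at least a count and a rate. If SAP 7.12 is followed as written, the report will say how many events were serious or device-related, but not how many subjects had a broken, loose or infected implant, or a dislocated or revised one. Someone would have to count them from the listing, with no prespecified rule for assigning descriptions to types.

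The lack of a cohort split adds to this. The second cohort was enrolled because device testing and inspection changed during the study, so a reader will want each failure type before and after the change. The plan compares the cohorts only on the composite, and only in per-protocol subsets that leave out treated subjects with significant deviations.

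**Working it through.** **1. Where each named event type would be reported**

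The composite in SAP 7.4 and 7.9 fails a subject if the device is removed or revised, if a device-related complication needs components replaced, removed or augmented, or if there is chronic dislocation.

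| Event type | Own summary in SAP 7.12 | Enters the composite |
|---|---|---|
| Infection | No | Only if it leads to removal or other component surgery |
| Loss of fixation | No | Only if it leads to removal or other component surgery |
| Breakage | No | Only if it leads to removal or other component surgery |
| Dislocation | No | If chronic, or if it leads to component surgery |
| Revision | No | Yes, but not separated from the other ways to fail |

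Protocol 7.0 keeps a subject in follow-up after surgery on the shoulder if the implant components are retained. So a breakage or loosening without component surgery is not a composite failure. It counts in the AE totals of SAP 7.12, where its type cannot be seen.

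**2. Cohort sizes (Protocol 11.3, SAP 6.1)**

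The original cohort is 150. The size of the new cohort reproduces from the one-sample formula at one-sided alpha 0.05:

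n = p(1 − p)(z₀.₉₅ + z₀.₈₀)² / δ² = 0.961 × 0.039 × (1.645 + 0.842)² / 0.033² = 212.8

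The plan states 212. Allowing for 10% loss, 213/0.9 = 236.7, so 237, and 150 + 237 = 387. These sizes are not in dispute here.

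**3. What the missing tables could show**

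The documents give no breakage rate, so every count and rate below is an assumption except 3.9%. That figure is 100 − 96.1, the composite failure rate implied for the original cohort. Intervals are exact (Clopper-Pearson) 95%.

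| Assumed events | Rate | 95% interval |
|---|---|---|
| 0/150 | 0% | 0 to 2.43% |
| 0/237 | 0% | 0 to 1.54% |
| 0/387 | 0% | 0 to 0.95% |
| 6/150 (before) | 4.0% | 1.48 to 8.50% |
| 6/387 (pooled: 6 before, 0 after) | 1.55% | 0.57 to 3.34% |

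If six breakages occurred before the change and none after, pooling would turn 4.0% and 0% into 1.55%.

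**4. What a formal cohort contrast could show**

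Power of a two-sided 5% Fisher test, 150 against 237, by full enumeration:

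| Assumed before | Assumed after | Power |
|---|---|---|
| 2% | 0.5% | 18% |
| 2% | 0% | 35% |
| 3.9% | 1% | 40% |
| 3.9% | 0.5% | 61% |
| 6% | 1% | 75% |
| 3.9% | 0% | 84% |

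As a rough check on precision, the Wald half-width is 1.96 × √(p₁(1 − p₁)/150 + p₂(1 − p₂)/237). For 2.0% against 0.5% it is 2.4 points around a difference of 1.5. The expected counts are 150 × 0.02 = 3 and 237 × 0.005 = 1.2, too few to trust that approximation, so exact intervals are preferable.

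All of this uses full enrolment. Under the protocol's 10% annual attrition the original cohort falls to 150 × 0.9¹⁰ = 52 at ten years. With zero events in 52 subjects the exact upper limit would be 1 − 0.025^(1/52) = 6.8%.

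**The case against.** The strongest reply is that much of this is reported already. SAP 7.12 uses several axes, among them relationship to device and to procedure, so it would be wrong to infer that safety is tabulated by regulatory class alone. It would also be wrong to infer that the named endpoints have no planned estimate at all. Revision largely drives the composite, which gets exact intervals at 2, 5 and 10 years and, if data allow, a Kaplan-Meier curve. Chronic dislocation enters it too, and the composite is summarised by cohort. All this stands. It narrows the gap to separate rates by type, and to events without component surgery.

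A second reply concerns the cohorts. A reader might infer that the inspection change was aimed at breakage or loss of fixation, and that the plan therefore fails to answer the study's own question. The documents do not support this. They do not say which failure mode the change targeted, Protocol 11.9 promises no cohort split for event types, and the sample-size reasoning in Protocol 11.3 is about the success rate. The by-cohort tables are thus a sensible addition, not an unmet commitment. A formal test would also be weak unless the drop were large.

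Third, the SAP cites table, figure and listing shells that are not among the documents here. They might hold an event-type table, and the listing allows a hand count. Neither replaces a specification in the SAP, which defines no event-type variable.

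**Conclusion.** The point holds in this form: five event types are named as safety endpoints to be analysed, and the SAP specifies no summary by type for any of them, overall or by cohort. For revision and chronic dislocation the loss is partial, because they reach the composite. For breakage, loss of fixation, infection and non-chronic dislocation that do not lead to component surgery, nothing beyond undifferentiated AE totals and the listing is planned.

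The primary non-inferiority test is unaffected. This should be corrected because the analysis section does not analyse the endpoints that the same plan names. The size of what would be missed cannot be taken from the documents. The illustration of 4.0% and 0% merging into 1.55%, and power running from 18% to 84%, rest on assumed rates and full enrolment. They show that by-cohort description is feasible and that a confirmatory contrast is not a realistic aim for small differences.

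**What to change.** - **SAP 7.4:** derive a flag for each of the five event types, with a written rule for assigning AE descriptions to types. Derive a cohort flag (enrolled before or after the proof-testing and inspection change) for all treated subjects, not only for the per-protocol subsets.
- **SAP 7.12:** for each type report the number of events, and the number and percentage of subjects with an exact 95% interval, on the safety population, overall and by cohort.
- **SAP 7.12, where data allow:** add cumulative incidence at 2, 5 and 10 years, because follow-up and attrition may differ between cohorts. State the censoring rules, including how revised subjects are handled, since Protocol 7.0 withdraws them.
- **Labelling:** call the cohort results descriptive, with no non-inferiority or superiority claim.

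The cost is the work of assigning AE descriptions to types, the censoring rules, and a few extra tables from AE data already collected. The cohort intervals will be wide, and more so at ten years.
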